3.13 Measures of process

At three monthly intervals insulin regime will be recorded in order to measure the total dose of insulin.

At 6 months from baseline, social support will be measured with the *Significant Other Scale* ⁶⁶ to assess how it mediates the effect of health technologies on glycaemic control.

3.14 Ethical arrangements

Risks and anticipated benefits: CBT and MI are extremely safe interventions with negligible risks for the trial participant and for society. If either technology was effective, this could improve the care that patients with T1DM receive safely and with little extra cost to the NHS. Informing potential participants: psychological interventions are safe. Consent: All patients will be asked to give written informed consent. They will be given a brief summary of the current evidence for psychological interventions in diabetes and the rationale behind randomisation. All patients will be given a copy of their signed consent form and information sheet and one will be filed in the medical notes. Confidentiality: The database that contains the patients' names addresses and unique identifier will be accessed only by the research co-ordinator and the principal investigator. All other

data will be stored separately where patients will be identified by their unique identifier. Time period: retention of trial documentation is estimated at ten years.

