3.1 Hypotheses

Main hypothesis: Motivational Interviewing (MI) plus Cognitive Behaviour Therapy (CBT) will be more effective than usual care at improving glycaemic control in T1DM at 12 months follow up.

Subsidiary hypotheses

(i) Motivational interviewing will be more effective than usual care at improving glycaemic control at 12 months follow up.

(ii) MI plus CBT will be more effective than MI alone at improving glycaemic control at 12 months follow up.

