3.12 Outcome

Main outcome: this will be the glycaemic control, measured by HbA_{1c} at 12 months follow up. However, we will also check patients HbA_{1c} at 3, 6 and 9 months to measure whether improvement is stepwise, gradual or sustained.

Subsidiary outcomes at 12 months follow up to measure change:

1. Biological: diabetes complications status will be repeated if not done 3 months before or after end of 12 month follow up at annual diabetes review. Body mass index and blood pressure will be measured.

2. Diabetes specific cognitions: The Diabetes Specific Health Beliefs-Experience of Treatment and Benefit Barriers; Fear of Hypoglycaemia questionnaire; and Beliefs about Medicine Questionnaire.

3. Diabetes specific behaviour: The Summary of Diabetes Self – Care Activities..

4. Psychiatric morbidity: *Primary Care Evaluation of Mental Disorders (PRIME-MD PHQ);* *GHQ-12*; the Alcohol Use Disorders Identification Test and the Life Events questionnaire.

5. Quality of life: The Short Form-36; the EuroQOL; and the DQOL.

6. Costs: Client Services Receipt Inventory

7. Social support: from family, friends and health professionals will be examined by the *Significant Others Scale*.

8. Adverse events checklist. A list of adverse events if and when they are reported will be compiled. Potential adverse events presently identified include any death, psychiatric admission, medical admission, onset of complication secondary to rapid glycaemic control (painful neuropathy, accelerated retinopathy, hypoglycaemic episodes).

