3.15 Proposed sample size

We will assume that the baseline HbA_{1c} is approximately 9.0% ⁶. We will assume that the post CBT or post MI mean will be 8% based on the evidence that a reduction of 1% in HbA_{1c} is associated with a clinically and statistically significant reduction in risk of developing diabetes complications.⁶ We will assume that control mean HbA_{1c} will be 8.8% (based on the principle that participating in the study as a control can have a slight improvement on glycaemic control.⁶ We further assume that the standard deviation of the changes is approximately equal to 1.65 based on the average standard deviation of the change scores in a RCT of cognitive analytic therapy at 3 month follow up from end of intervention period.³¹ We therefore require 90 subjects per group to achieve 90% power to detect the difference in mean change between two groups using a t-test with a 5% level of significance. Allowing for a 20% drop-out rate, we therefore need 113 subjects for each arm giving a total of 339 participants.

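### Section 3.14 fixes an unqualified message of safety for potential participants, while section 3.12 lists harms foreseen if glycaemic control improves rapidly

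*Protocol*

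**What the plan says.** Section 3.14 (Ethical arrangements) treats risk in two separate items. The first, on risks and benefits, is the investigators' own appraisal: "CBT and MI are extremely safe interventions with negligible risks for the trial participant and for society". The second, on informing potential participants, is a single statement: "Informing potential participants: psychological interventions are safe". For consent, the section adds that patients receive a short summary of the evidence on psychological interventions, an explanation of why allocation is random, and a copy of the information sheet. None of the consent content described there is a risk.

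Section 3.12 (Outcome), item 8, sets up an adverse events checklist. Alongside death and psychiatric or medical admission, it includes "onset of complication secondary to rapid glycaemic control (painful neuropathy, accelerated retinopathy, hypoglycaemic episodes". It presents these as potential events that have already been identified.

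The main hypothesis in section 3.1 is that MI plus CBT will "be more effective than usual care at improving glycaemic control in T1DM at 12 months follow up". A subsidiary hypothesis says the same of MI alone.

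**The concern.** The section that governs consent gives an unqualified assurance. The outcome section of the same protocol names specific harms that the team thinks possible. Those harms are not incidental to the trial: they are tied to a change in glycaemic control, which is what both active treatments set out to achieve. Someone drafting or checking the information sheet against 3.14 alone would find nothing requiring these events to be mentioned.

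Two things are at stake. The first is disclosure: a harm foreseen in the protocol should be reflected in the protocol's own statement of what participants are told, even if it is thought to be uncommon. The second is ascertainment. Item 8 compiles events as they are reported, so its yield depends partly on participants recognising that an event is relevant to the trial.

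**Working it through.** The point is textual, so the sections are set side by side. The planned HbA1c figures are checked only to show what effect the trial intends.

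**1. The two statements**

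| | Section 3.14 | Section 3.12, item 8 |
|---|---|---|
| Purpose | Risk appraisal and message to participants | List of events to record |
| Content | Safe, without qualifier; risk appraised as negligible | Painful neuropathy, accelerated retinopathy, hypoglycaemic episodes |
| Condition | None | Secondary to *rapid* glycaemic control |
| Frequency given | None | None |

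No figure contradicts another, because neither section gives one. The conflict is between an unconditional assurance and a conditional list of foreseen harms.

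**2. Are the harms connected with what the trial intends?**

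Inputs from section 3.15:
- Baseline: "We will assume that the baseline HbA_{1c} is approximately 9.0" per cent.
- Active arms: "We will assume that the post CBT or post MI mean will be 8" per cent.
- Controls: "We will assume that control mean HbA_{1c} will be 8.8" per cent.
- Spread: "the standard deviation of the changes is approximately equal to 1.65".

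Intended mean fall, active arms: 9.0 − 8.0 = 1.0 point. Controls: 9.0 − 8.8 = 0.2 point. Between-group difference: 1.0 − 0.2 = 0.8 point.

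The protocol's sample size confirms that these are the planning values. With a two-sided 5% level (sidedness is assumed; the protocol does not state it) and 90% power:

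n per group = 2 × (1.960 + 1.282)² × 1.65² / 0.8² = 2 × 10.51 × 2.7225 / 0.64 ≈ 89.4, rounded up to 90.

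An exact t-test calculation gives 90.4, which agrees with the stated 90 to within rounding. Allowing for 20% drop-out, 90 / (1 − 0.20) = 112.5, rounded up to 113 per arm. Then 3 × 113 = 339 in total, of whom 2 × 113 = 226 are in the two active arms. All the stated figures are reproduced.

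A larger fall in HbA1c in the active arms is therefore the planned effect. Nothing in 3.1, 3.10 or 3.15 says that the fall should be rapid. Section 3.12 measures HbA1c at 3, 6 and 9 months precisely because the shape of any improvement over time is left open. Rapid improvement is thus a possible form of the intended effect and no more than that.

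**3. How would the three named events be found?**

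- *Retinopathy and neuropathy.* Section 3.12, item 1, repeats complication status around 12 months unless it was recently done at annual review. The baseline methods in 3.8 are retinal photography and vibration-perception threshold. These two complications do not depend on spontaneous report alone.
- *Pain from neuropathy.* A vibration threshold does not record pain.
- *Hypoglycaemic episodes.* The fear of hypoglycaemia questionnaire measures worry, not episodes.

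For the last two, capture rests largely on what participants report. That an unqualified assurance would reduce reporting is a reasonable inference; the protocol contains no evidence on it.

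**The case against.** The strongest reply is that a monitoring checklist is not a statement of risk. Item 8 also lists any death and any admission, and recording such events is compatible with judging the treatments to be of very low risk. This stands as far as it goes: listing an event does not show that it is likely. It does not remove the mismatch, because a small foreseen risk is still one that the consent section should acknowledge.

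Several stronger readings are tempting, and the documents do not support them:

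- *That participants will be told the risks are negligible.* That phrase belongs to the investigators' appraisal. The item on informing participants says only that the interventions are safe.
- *That participants will consent without knowing of these harms.* The information sheet is not available to this review and may name them. One line in a protocol is not the full content of that sheet.
- *That the active arms are designed to produce the condition that causes the harms.* The stated aim is better control at 12 months. The listed harms are tied to rapid control.
- *That the active arms carry five times the risk.* The ratio 1.0 / 0.2 = 5 compares assumed mean HbA1c falls. It says nothing about speed of fall or event rates.
- *That admissions follow from treatment success.* Item 8 lists them separately from the complications of rapid control.

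It is also fair to say that safeguards exist. Complications are rechecked around 12 months, usual care in every arm includes an annual review and aims to avoid troublesome hypoglycaemia, and a data monitoring and ethics committee is to meet at least twice a year. These limit the consequences for detection but do not change what 3.14 says.

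**Conclusion.** The point holds as an inconsistency between sections 3.14 and 3.12, item 8. The protocol's message to potential participants is unqualified, while its adverse event list names painful neuropathy, accelerated retinopathy and hypoglycaemic episodes as foreseen complications of rapid glycaemic control, a possible consequence of the effect that the trial seeks.

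Its size is modest. The message concerns all 339 planned participants, since consent precedes allocation. It does not touch the estimate, the sample size or the analysis. The risk itself cannot be quantified from the protocol.

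The conclusion rests on reading the item in 3.14 as the protocol's statement of what participants are told. If the information sheet already names these events, what remains is a correction to the protocol so that it matches the sheet. A reader should not infer from this point that informed consent failed, or that the active arms have been shown to be hazardous.

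**What to change.** Reconcile section 3.14 with section 3.12, item 8:

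1. Replace the unqualified assurance in 3.14 with a statement that the sessions carry little direct risk, but that rapid improvement in glycaemic control may bring the events listed in item 8. Keep the word *rapid*. Attributing these harms to improved control in general would go beyond item 8 and sit badly with 3.15, which cites a lower risk of complications after a 1% reduction in HbA1c.
2. Qualify the investigators' risk appraisal in the same section so that it refers to item 8.
3. Require the participant information to name those events, if it does not already, and to ask participants in all three arms to report them to the research team. Asking all arms alike keeps reporting comparable between groups.

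The cost is a protocol wording amendment, a revised information sheet if the present one is silent, and a slightly less reassuring consent message. No treatment, clinical rule, sample size or analysis changes.

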3.15 Proposed sample size

We will assume that the baseline HbA_{1c} is approximately 9.0% ⁶. We will assume that the post CBT or post MI mean will be 8% based on the evidence that a reduction of 1% in HbA_{1c} is associated with a clinically and statistically significant reduction in risk of developing diabetes complications.⁶ We will assume that control mean HbA_{1c} will be 8.8% (based on the principle that participating in the study as a control can have a slight improvement on glycaemic control.⁶ We further assume that the standard deviation of the changes is approximately equal to 1.65 based on the average standard deviation of the change scores in a RCT of cognitive analytic therapy at 3 month follow up from end of intervention period.³¹ We therefore require 90 subjects per group to achieve 90% power to detect the difference in mean change between two groups using a t-test with a 5% level of significance. Allowing for a 20% drop-out rate, we therefore need 113 subjects for each arm giving a total of 339 participants.

3.16 Statistical analysis

Data will be entered using SPSS and analysed using STATA. The success of randomisation will be assessed by comparing baseline characteristics. The difference in mean reduction of HbA_{1c} between the CBT, MI and control groups will be estimated using a linear mixed model incorporating fixed effects of group, time and group by time and a random effect for subjects. All available data will contribute to the analysis including data on subjects who dropped out or withdrew from the trial (intention to treat analysis). The same analysis will be used to identify other predictors, such as presence of diabetes complications and psychiatric morbidity and effect modifiers such as social support. Secondary outcomes (illness perceptions and diabetes specific behaviours) will be analysed using linear mixed models and generalised linear mixed models for dichotomous outcomes. We will model the change in mean HbA1c over time using a linear trend and a quadratic one if needed. The change over time is reflected by the linear trend, "the effect of time", and a treatment effect would correspond to a group by time interaction. A comparison of participants and non-participants of the RCT will be performed on socio-demographic data available from the databases. A comparison of the baseline characteristics of completers and non completers will be done. Economic analysis: Total average costs will be linked with the main outcome (improvement in HbA_{1c}) for each group in the form of a cost-effectiveness analysis. A cost-utility analysis will be conducted on the SF-36. This will offer a simpler decision rule and allow explorations of cost per quality-adjusted life-year (QALY) gained.

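### The single subject random effect in the HbA1c model assumes equal correlation between all visits; if correlation decays or patients' slopes differ, the standard error of group by time is understated

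*Protocol*

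**What the plan says.** Section 3.12 makes the main outcome glycaemic control "measured by HbA_{1c} at 12 months follow up" and adds that "we will also check patients HbA_{1c} at 3, 6 and 9 months". With the baseline value (section 3.8) there are five visits: 0, 3, 6, 9 and 12 months.

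Section 3.16 specifies a linear mixed model "incorporating fixed effects of group, time and group by time and a random effect for subjects". Time enters "using a linear trend and a quadratic one if needed", and "a treatment effect would correspond to a group by time interaction". The section names one random effect. It mentions no random slope, correlated residuals or robust standard error.

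The only significance level is in section 3.15, where the trial is sized for a comparison of mean change "using a t-test with a 5% level of significance".

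**The concern.** One random effect per subject with independent residuals gives the same correlation between any two visits and no variation in slope within an arm. The model then measures the error in the slope by the pooled within-patient scatter. If patients drift apart over the year, the scatter that matters for a slope, or for a 12-month change, is larger than that pooled figure.

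Other parts of the protocol suggest that patients will drift apart. Section 3.10 describes therapy adapted to each patient. Section 3.12 asks what shape the improvement takes. Section 3.16 plans to look for predictors and effect modifiers.

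The main hypothesis and both subsidiary hypotheses in section 3.1 concern HbA1c and rest on this model. An understated standard error would raise the false-positive rate above 5% and make the confidence intervals too narrow.

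**Working it through.** **The plan's own figure.** Section 3.15 assumes means of 8.0% and 8.8% (difference 0.8) and that "the standard deviation of the changes is approximately equal to 1.65". At two-sided 5% and 90% power:

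n = 2 × (1.960 + 1.282)² × (1.65/0.8)² ≈ 89.4, so 90 per group; 90/0.8 = 112.5, so 113; 3 × 113 = 339.

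This agrees with "We therefore require 90 subjects per group to achieve 90% power" and with the stated total. It is a t-test on change with its own SD and does not use the mixed model.

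**Method.** Centre the five visits in 3-month units: c = (−2, −1, 0, 1, 2), sum of squares 10. Let V be the true covariance of one patient's five values.

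- True variance of a patient's fitted slope: c′Vc/10².
- Variance the random-intercept model reports: w/10, where w is the pooled within-patient variance.
- SE ratio r = √(10w / c′Vc).
- Actual size of the nominal 5% test in large samples: 2 × [1 − Φ(1.96 r)].

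**Equal correlation ρ.** c′Vc = 10(1 − ρ) and w = 1 − ρ, so r = 1 and the size is 5.0%.

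**Random slopes.** Let slopes carry a share s of the variance of the 12-month change, the rest being independent residual. The total variance cancels:

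r² = (0.5 − 0.34375 s) / (0.5 + 0.125 s).

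For s = 0.25: 0.41406/0.53125 = 0.779, so r = 0.883 and the size is 8.4%.

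If the SD of 12-month change is taken as 1.65, a residual SD of 1.0 gives s = (2.7225 − 2)/2.7225 = 0.27 and a size of 8.6%.

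**AR(1), adjacent-visit correlation ρ.** c′Vc = 10 + 8ρ − 2ρ² − 8ρ³ − 8ρ⁴, and w = 1 − (4ρ + 3ρ² + 2ρ³ + ρ⁴)/10.

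For ρ = 0.8: c′Vc = 7.747 and w = 0.3446, so r = √(3.446/7.747) = 0.667 and the size is 19.1%.

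**Mixture: stable subject part 0.5, AR(1) part 0.3 with ρ = 0.6, noise 0.2.** The correlation falls from 0.68 at 3 months to 0.54 at 12. c′Vc = 0.3 × 11.315 + 0.2 × 10 = 5.395, and 10w = 10 × (0.3 × 0.5958 + 0.2) = 3.788. So r = 0.838 and the size is 10.1%.

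| Assumed truth | SE ratio | Actual size |
|---|---|---|
| Equal correlation | 1.00 | 5.0% |
| Slopes carry 10% of change variance | 0.95 | 6.2% |
| Slopes carry 25% | 0.88 | 8.4% |
| Slopes carry 50% | 0.76 | 13.4% |
| Slopes carry 75% | 0.64 | 21.1% |
| Mixture 0.5 / 0.3 (ρ 0.6) / 0.2 | 0.84 | 10.1% |
| Mixture 0.4 / 0.4 (ρ 0.7) / 0.2 | 0.81 | 11.3% |
| Mixture 0.3 / 0.5 (ρ 0.8) / 0.2 | 0.80 | 11.9% |
| AR(1), ρ 0.6 to 0.9 | 0.73 to 0.64 | 15.5% to 20.8% |
| Equal correlation 0.7, baseline SD 0.8 of later visits | 1.03 | 4.4% |
| Correlation rising with lag, 0.60 to 0.75 | 1.36 | 0.8% |

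**Simulation check.** Random-intercept REML fits with 113 per arm, 20% random monotone dropout and 1,500 runs gave 14%, 19% and 21% for AR(1) with ρ of 0.6, 0.8 and 0.9. They gave 8% and 15% for slope shares of 25% and 50%, and 5.6% under equal correlation (Monte Carlo standard error about 0.6 points).

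**Categorical time alone is not a cure.** With the same random intercept, the 12-month minus baseline contrast has size 7.5% at a 25% slope share, 7.6% for the first mixture and 15.0% for AR(1) with ρ = 0.9.

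**The case against.** The strongest reply is that the sentence in section 3.16 is protocol shorthand. It does not exclude correlated residuals or robust standard errors, and a statistical analysis plan that is not at hand may specify them. This stands in part: equal correlation follows only if the residuals are independent, which the protocol does not say. But the random part of the primary model is stated, in the singular, and its ordinary reading is a random intercept.

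The second reply is that the protocol gives no between-visit correlation, visit variance or slope variance. This stands in full. A reader might infer that the standard error is certainly too small and that the 5% test is invalid. The documents do not support that. Under equal correlation the test is correct in large samples, and the last two rows of the table are conservative. Nor is exact equal correlation required: any covariance with c′Vc = 10w gives 5%.

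The third reply is that the largest figures need strong inputs. At a change SD of 1.65, a size of 20.5% needs a residual SD of 0.6, with slopes carrying 74% of the change variance. A residual SD of 0.4 gives 26.6%, but slopes then carry 88%. Pure AR(1) with ρ = 0.6 leaves a 12-month correlation of only 0.13 and no stable patient component. This stands, and the milder rows are the better guide. The 1.65 itself comes from another trial, 3 months after its intervention ended, so using it for 12-month change is an assumption made here.

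A restricted entry range could make the baseline variance smaller, but this does not cancel the effect. With baseline SD at 0.8 of later visits, mild decay still gives about 9% to 12%, and AR(1) with ρ of 0.6 to 0.9 gives 14% to 19%.

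**Conclusion.** The point holds in conditional form, as something that should be fixed. The primary model as written relies on equal correlation at all lags and a common slope within each arm, and the linear group-by-time term is sensitive to both. If correlation decays mildly or slopes vary modestly, the true size of the nominal 5% test is about 8% to 11%, just under 12% for the heaviest mixture tried. With pure AR(1) or dominant random slopes it reaches about 20%. It is 5% under equal correlation, slightly below that with a smaller baseline variance, and well below only if correlation rises with lag.

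All these figures rest on assumed covariances, large-sample theory and independent residuals around the single random effect. It would also be wrong to infer a fault in the sample size: 90, 113 and 339 reproduce and do not depend on this model.

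**What to change.** In section 3.16, replace the single subject effect with one of these:

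- an unstructured within-subject covariance over the five visits (5 variances and 10 covariances, 15 parameters, which 339 patients can support);
- a random intercept and a random slope for each patient;
- the random intercept kept, with cluster-robust standard errors by subject.

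Each brings the size of the linear group-by-time test back to about 5% in large samples. The unstructured form assumes least and also covers a quadratic term or a visit-specific 12-month contrast. Robust standard errors repair the error bar, but where visits are missing the point estimate still leans on the equal-correlation working model.

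The cost is one sentence, a few more covariance parameters and usually somewhat wider intervals. Relative to the random-intercept interval, they widen by about 1/0.883 = 1.13 at a 25% slope share and 1/0.838 = 1.19 for the mildest mixture. If equal correlation is true, little is lost. Section 3.15 needs no change on this account.

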3.8 Baseline measures

Socio-demographic: data will be collected on age, sex, level of education, occupation, marital status, self report ethnicity.

Biological: HbA_{1c} (measured at screening); duration of diabetes; complications - retinopathy will be measured by retinal photography;⁵² neuropathy will be measured using the vibration-perception threshold⁵³ and nephropathy will be measured using an early morning urine sample for albumin-creatinine ratio.⁵⁴ Body mass index and blood pressure will be measured.

Diabetes specific cognitions: The *Diabetes Specific Health Beliefs-Experience of Treatment and Benefit Barriers* subscale for insulin treated diabetes will be used to measure the patient's perspective of adherence to the diabetes regimen.⁵⁵ *Fear of Hypoglycaemia* questionnaire⁴⁶ will be used as worries are not adequately measured by the *Diabetes Specific Health Beliefs*. The Beliefs about Medicine Questionnaire will be used to elicit beliefs about the use of insulin.⁶⁷

Diabetes specific behaviour: The *Summary of Diabetes Self –Care Activities* questionnaire measures frequency of adherence to eating habits, exercise levels, glucose monitoring and medication.⁵⁶

Psychiatric morbidity: This will be measured using the *Primary Care Evaluation of Mental Disorders (PRIME-MD PHQ)*⁵⁷ which is a self report measure for depressive, anxiety, alcohol, somatoform and eating disorders and using the *General Health Questionnaire-12*.⁶⁸ The *Life Events Questionnaire*⁶⁹ will be used to determine perceived stress and the World Health Organisation's *Alcohol Use Disorders Identification Test* to measure alcohol consumption.⁷⁰

Quality of life: The *Short Form-36* ⁵⁸ will be used which has been used extensively in diabetes. The *EuroQOL*⁷¹ will be used in order to conduct a cost-utility analysis, and the *Diabetes Quality of Life* measure to look at diabetes-specific themes. ⁷²

Costs: *Client Services Receipt Inventory*⁵⁹ gives a detailed description of service use patterns, medication (including insulin), employment and household family responsibilities in the previous 3 months.

Social support: from family, friends and health professionals will be examined by the *Significant* Others Scale.⁶⁶

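### The HbA1c model in 3.16 makes no use of the pre-randomisation HbA1c as a covariate or common baseline, and so gives up a modest amount of precision at no saving

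*Protocol*

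**What the plan says.** Section 3.12 defines the main outcome: "this will be the glycaemic control, measured by HbA_{1c} at 12 months follow up". It adds that "we will also check patients HbA_{1c} at 3, 6 and 9 months". Section 3.8 lists HbA1c among the baseline biological measures, "measured at screening", and 3.9 places randomisation after that.

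Section 3.16 fixes the analysis: "The difference in mean reduction of HbA_{1c} between the CBT, MI and control groups will be estimated using a linear mixed model". It specifies the terms of that model as "incorporating fixed effects of group, time and group by time and a random effect for subjects". It models time as a linear trend, quadratic if needed, and concludes that "a treatment effect would correspond to a group by time interaction". The terms listed for the HbA1c model include no baseline HbA1c covariate and no common baseline mean.

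Section 3.15 works on the same scale. It takes an SD of change of 1.65 and powers a comparison of mean change between two groups "using a t-test with a 5% level of significance".

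**The concern.** A reduction is measured from a baseline. The natural reading of 3.16 is therefore that baseline HbA1c is one of the modelled responses, that the group main effect lets it differ freely by arm, and that the interaction is a difference in change from baseline.

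The arms are formed after the baseline is measured, so their true baseline means are equal. Fitting a separate baseline mean for each arm estimates a quantity known to be zero, and the noise in that estimate passes into the treatment effect. Put another way, a change score fixes the slope of follow-up on baseline at 1. If the true slope is lower, the change score subtracts too much of any chance baseline difference.

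What is at stake is precision. The same model serves the main hypothesis and both subsidiary hypotheses in 3.1.

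**Working it through.** **Inputs from the protocol.** Section 3.15: baseline mean 9.0%; post-treatment mean 8.0%; control mean 8.8%, so the difference is 0.8; SD of change 1.65; 5% level; 90% power; 90 per group; 20% drop-out. Section 3.7: entry HbA1c 8.2–12%, changed to 8.2–15% in the appendix. A two-sided test is assumed, since sidedness is not stated.

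**The plan's own figure.** n = 2(1.960 + 1.282)² × 1.65²/0.8² = 89.4, so 90 per group. 90/0.8 = 112.5, so 113 per arm and 339 in all. This reproduces. Power at 90 per arm is 90.2% by the normal approximation and 89.9% by the noncentral t.

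**Formula.** Let s0 be the baseline SD and b the slope of 12-month HbA1c on baseline. The variance of change splits into the residual variance given baseline plus s0²(1−b)². Adjustment removes the second part, so

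proportional reduction in variance = [s0(1−b)]²/1.65², with 1.65² = 2.7225.

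**Assumed ranges.** The protocol gives neither s0 nor b. Power is by the noncentral t at 90 per arm, for a difference of 0.8, with SD 1.65 × √(1 − reduction).

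| s0 | b | [s0(1−b)]² | Reduction | Power |
|---|---|---|---|---|
| 0.8 | 0.3 | 0.3136 | 11.5% | 93.0% |
| 0.8 | 0.5 | 0.1600 | 5.9% | 91.5% |
| 0.8 | 0.7 | 0.0576 | 2.1% | 90.5% |
| 1.0 | 0.3 | 0.4900 | 18.0% | 94.7% |
| 1.0 | 0.5 | 0.2500 | 9.2% | 92.4% |
| 1.0 | 0.7 | 0.0900 | 3.3% | 90.8% |

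**A second route.** Assume a follow-up SD of 1.6, wider than baseline because entry is restricted on HbA1c. With the SD of change held at 1.65, b = (s0² + 1.6² − 1.65²)/(2s0²).

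- s0 = 1.0: b = 0.8375/2 = 0.419; reduction (0.581)²/2.7225 = 12.4%; power 93.3%.
- s0 = 1.4: b = 1.7975/3.92 = 0.459; reduction (1.4 × 0.541)²/2.7225 = 21.1%; power 95.4%.

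**How large s0 can be.** With mean 9.0 on 8.2–12, the largest possible SD is √(0.8 × 3.0) = 1.55. On 8.2–15 it is √(0.8 × 6.0) = 2.19. Each is reached only if every patient sits at one of the two limits. An s0 of 1.4 is therefore towards the top of what the protocol's own assumptions allow on the narrower range.

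**Scope of the formula.** It is exact for a baseline-to-12-month change contrast. Under the linear trend in 3.16 the effect is a slope difference over all visits. That is still a within-patient contrast with a free baseline difference, so the same kind of loss applies, though not by exactly these percentages.

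**The case against.** The strongest reply is that nothing here is wrong. Under randomisation the interaction is unbiased and its test valid. Sections 3.15 and 3.16 both work with change, and the planned 90% power is met. All of that stands: this is a choice between accepted analyses, and a reader who inferred that the trial is underpowered would be mistaken.

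A reader might also infer a much larger gain from the textbook formula with equal variances, where the variance ratio is (1+r)/2 for a baseline to 12-month correlation r. At r = 0.5 that gives a 25% reduction and 96% power. The protocol's figures do not support it. With an SD of change of 1.65, equal variances require an SD of 1.65/√(2(1−r)), which is 1.65 at r = 0.5 and 2.13 at r = 0.7. Both exceed the ceiling of 1.55 for 8.2–12%. On 8.2–15% the second almost reaches the ceiling of 2.19.

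Another tempting reading is that selecting patients at 8.2% or above biases the comparison through regression to the mean. It does not. Selection precedes randomisation and applies equally to all arms, so it cancels in expectation from the between-arm contrast.

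The pilot in 3.18 points to a small gain. It reports 12.7 (SD 2.6) before and 11.6 (SD 2.9) after in five patients, p = 0.07. If that is two-sided, t on 4 df is about 2.46, the SD of change is 1.1 × √5/2.46 = 1.0, and r = (2.6² + 2.9² − 1.0²)/(2 × 2.6 × 2.9) = 0.94, so b is about 1.05 and almost nothing is gained. Five patients with eating disorders and a mean far above the 9.0% assumed for the trial are weak evidence, but they show that the low end of the range is possible.

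Finally, 3.16 does not say outright that baseline is a response. If it is not, the interaction captures only divergence after 3 months and misses any benefit already present by then. A separate analysis plan might add covariates, but the effect definition that the protocol itself fixes does not include them.

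**Conclusion.** The point holds as a modest loss of efficiency, with no bearing on validity. Using baseline HbA1c would reduce the variance of the 12-month contrast by about 2% to 18% for s0 of 0.8 to 1.0 and b of 0.3 to 0.7, and by 12% to 21% for s0 of 1.0 to 1.4 with a follow-up SD of 1.6. Power at 90 per arm would move from 90% to between about 90.5% and 95%.

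These sizes rest on assumed values of s0 and b and on the protocol's SD of change of 1.65. The gain shrinks to nothing as b approaches 1. In large samples adjustment does not lose precision, so the change is worth making even though its benefit may be small.

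**What to change.** In 3.16, keep the linear mixed model and state one of two forms:

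- baseline HbA1c stays among the responses, with its mean constrained to be equal across the three arms; or
- HbA1c at 3, 6, 9 and 12 months is the response, with baseline HbA1c and baseline by time as covariates.

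In either case, name the adjusted 12-month difference between arms as the treatment effect, which also ties the analysis to the main outcome in 3.12. The sentence should say explicitly whether baseline is a response or a covariate.

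The cost is one sentence. It needs no extra data, visits or patients. Section 3.15 can stay at 113 per arm and 339 in all, which becomes slightly conservative.
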